7. DATA AND SAFETY MONITORING PLAN (DSMP)

7.A. Summary of DSMP

The overall organization of the DSMP aims to monitor this research protocol with emphasis on subject safety and data integrity. To this end, the DSMP outlined below will: 1) monitor the progress of the trial and the safety of participants, 2) assure compliance with requirements regarding the reporting of adverse events, 3) assure that any action resulting in a temporary or permanent suspension of the trial is reported to the DCC, ChiLDREN Steering Committee and NIDDK, and 4) assure data accuracy and protocol compliances. General monitoring guidelines have been developed by ChiLDREN to aid implementation of the DSMP, which will systematically monitor for:

- Verification that subject consent for study has been properly obtained and documented ensuring compliance with standards for protection of human subjects
- Verification that research subjects entered into the study meet inclusion and exclusion criteria
- Verification that the study is conducted in compliance with the protocol
- Verification of accuracy of the data collected
- Verification that all essential documentation required for good clinical practice guidelines are present, current, and appropriately filed.
- Verification of subjects completing the study

Particular attention will be given to monitoring subject safety issues. To this end, a Study Medical Safety Officer will be assigned for this clinical trial, and notification forms have been developed to expedite and facilitate the reports of serious adverse events. The DSMP will be overseen by the NIDDK and the Data and Safety Monitoring Board (described below).

7.B. Adverse events (AE) and Serious Adverse Event (SAE)

7.B1. Adverse events (AE) – Overview

Uncontrolled clinical trials of corticosteroid therapy following portoenterostomy in infants with biliary atresia reported collectively over 75 subjects with biliary atresia and over 100 episodes of corticosteroid treatment⁴⁶⁻⁴⁹. Regimens have included varying doses, durations, and times following portoenterostomy; no serious complications were reported. Adverse events in these studies, however, may not have been identified because of the small number of subjects included in individual studies or because adverse events may not have been systematically documented. Therefore, to monitor for potential adverse effects appropriately, we will systematically monitor all subjects at each scheduled visit. Subjects will be followed until complete/adequate resolution of an adverse event is documented. We will continue the evaluation of adverse events if a subject withdraws or is prematurely discontinued from participation in the study for any reason. The list of potential expected adverse effects was developed based on information from a pharmacology textbook and reviews of the published results clinical trials of dexamethasone to prevent chronic lung disease in over 1000 very-low-birth weight premature infants⁴⁵. Notably, some of the potential adverse effects of corticosteroids may also be present in infants with biliary atresia due to the natural progression of disease to biliary cirrhosis, such as gastrointestinal bleeding, growth impairment, and impaired response to routine immunizations. Therefore, it is important in this study that the frequency, severity and types of adverse effects, AEs and SAEs be compared between infants receiving study drug and those receiving placebo.

7.B2. Grading of AEs

An AE is any unfavorable or unintentional sign (including abnormal laboratory findings), symptom, or disease temporally associated with the use of a medicinal product, whether or not considered related to the medicinal product. Grading of AEs will be based on the National Cancer Institute-Common Terminology Criteria for Adverse Events⁷⁷⁻⁷⁹. Severity of AEs is outlined below:

- Grade 1: Mild adverse event
- Grade 2: Moderate adverse event
- Grade 3: Severe adverse event
- Grade 4: Life-threatening or disabling adverse event
- Grade 5: Death related to adverse event

7.B3. Serious Adverse Events (SAE)

In this study, an SAE is defined as any clinical adverse event or abnormal laboratory test value that is associated with events that could threaten a subject's life or functioning,

irrespective of the study arm (corticosteroids or placebo) to which the subject was assigned. The term SAE is not intended as a measure of severity or intensity⁷⁷⁻⁷⁹. Thus, an AE should be considered a SAE if it results in any of the following:

- Death
- Is life-threatening (subject was at risk of death as a result of the event; it does not refer to hypothetical risk of death if the event had been more severe)
- Requires insubject hospitalization or prolongation of an existing hospitalization
- Results in persistent or significant disability/incapacity
- A congenital anomaly/birth defect
- Is medically significant or requires intervention to prevent one or other of the outcomes listed above

7.C. AE and SAE Reporting Plan

An investigator from the DCC will serve as the Medical Safety Officer. He/she will carry a pager so that all SAEs may be reported promptly. The DSMB will review all AEs and SAEs during their regularly scheduled meetings, or on an expedited basis as determined by the NIDDK Program Director or Chair of the DSMB, according to the ChiLDREN policy manual.

All unexpected adverse events (UAEs) are reported to the DCC by completion of the Adverse Events Form by the study site into the secure ChiLDREN website. This triggers an email message to the Medical Safety Officer to check the website for the report; no personal identifying or medical information is contained in the email message.

All SAEs as defined previously require expedited event notification within 24 hours of occurrence or identification to the DCC. Expedited event notification is completed through web entry of the Adverse Events Form. Web entry generates an immediate email to the Medical Safety Officer with only the subject identification number in the message. The Medical Safety Officer then logs into the secure website to see the report of the event. In addition to web entry of the SAE, the Medical Safety Officer may be contacted for any questions or clarifications regarding classification of the event. Paging the Medical Safety Officer is not required as part of the expedited notification process, however may be used if any difficulty is encountered in the web-based notification system. Completing the web entry of the AE form will automatically send e-mail notification to the Medical Safety Officer, NIDDK Program Director, DCC PI, and Project Manager. Fax cover sheets are provided if there is a need to fax supporting information per request of the Medical Safety Officer or NIDDK Program Director. Once the Medical Safety Officer reviews the information submitted on the AE form, the clinical site will be contacted if additional information is required in order to draft a preliminary report of the SAE. Once completed, the preliminary report will be sent to the, the report will then be sent to the NIDDK Program Director, clinical site PI, DCC PI, Project Manager, and Chair of the DSMB.

Once the SAE is resolved, a final report is generated by the Medical Safety Officer. The Medical Safety Officer will send the final report to the NIDDK Program Director, clinical site PI, and the DCC PI and Project Manager. All SAE reports will go the DSMB for review. The NIDDK Program Director and the Chair of the DSMB will decide if any individual SAE

warrants notification to the FDA and to the IRB's of all participating ChiLDREN clinical sites.

The clinical site at which the SAE occurred is responsible for expedited reporting of the SAE to their respective IRB. Each site is responsible to report all AE's to their IRB according to its AE reporting policy and procedures.

Updates to SAEs are submitted to the DCC through web entry of AE form. An update report is generated through the same process that the original SAE report was entered. Updates to the AE form should be made until an outcome and end date for the event are known or if study participation ends.

The Medical Safety Officer will submit an expedited report to the FDA of an SAE when the SAE is unexpected and may be related (even remotely) to the study drug.

7.D. Monitoring and Management for Specific AEs

Several side effects of corticosteroids are anticipated in the subjects randomized to corticosteroid treatment. The following section outlines the plan for monitoring and management of these AEs. This monitoring will be conducted after portoenterostomy however before the first dose of study medication is given (to provide baseline data) and then at hospital discharge and at each scheduled follow up visit.

7.D1. Hypertension:

If a significant hypertension (systolic blood pressure ≥ 112 mmHg for infants <12 months of age)^{80a,b,c} is measured at least two times, and the subject is asymptomatic, a repeat blood pressure will be obtained within 24-48 hours. If the elevated blood pressure is resolved, no intervention will be necessary. If the repeat systolic blood pressure is ≥ 112 mmHg and the subject is asymptomatic, the study medication dose-reduction protocol (Section 4.F2) will be followed and a repeat blood pressure will be obtained within 48 hours; a mild AE will be reported⁷⁷. If the repeat systolic blood pressure remains ≥ 112 mmHg but the subject remains asymptomatic, anti-hypertensive monotherapy will be initiated (see below). If the hypertension persists beyond 48 hours, a second dose-reduction will be initiated and a second anti-hypertensive medication may be used (see below). If hypertension does not resolve within 48 hours or if the subject develops symptoms due to hypertension (e.g.: severe irritability, seizure) or as other life-threatening consequences, such as end-organ damage, drug or placebo will be tapered and discontinued (Section 4.F3), the subject will be referred to an emergency department, and additional anti-hypertensive treatment will be initiated. This will be reported as a SAE.

- a. Treatment choices for hypertension with BP ≥ 112 mmHg without symptoms
- Hydrochlorothiazide: 2 mg/kg/day given once or twice a day, or
 - Amlodipine: 0.2-0.4 mg/kg/day given once or twice a day, or
 - Captopril: 0.3-1 mg/kg/day given twice a day
 - Other site-specific treatment choice

b. Treatment choices for hypertension with BP \geq 112 mmHg with symptoms

- Nifedipine 0.25-0.5 mg/kg/ sublingual
- Labetolol: 1-3 mg/kg/hour IV
- Other site-specific treatment of choice

7.D2. Hyperglycemia

A random plasma glucose level will be obtained at the time of discharge and at follow-up visits (Table 6). If the random plasma glucose level is 200 mg/dL or higher the study subject will return within 24 hours for a repeat level. If the repeat glucose level is 200 mg/dL or higher⁸¹, a moderate AE will be reported and the study medication dose-reduction protocol (Section 4.F2) will be followed if the subject is asymptomatic. Persistent hyperglycemia above 200 mg/dL beyond 48 hours of dose reduction and associated with acidosis or change in mental status due to elevated serum osmolality will be considered a SAE, and the drug or placebo will be tapered and discontinued (Section 4.F3). If blood glucose is 150-200 mg/dL, treatment or observation will be directed by the local standard of care, including the option for study medication dose reduction (Section 4.F2).

7.D3. Hypokalemia

A random serum potassium level will be obtained at the time of hospital discharge and at follow-up visits (Table 6). If the potassium level is less than the lower limit of normal but above 3.0 mmol/L, a mild AE will be reported. A new serum K level will be obtained in 48 hours. If the potassium level is less than 3 mmol/L but \geq 2.5 mmol/L, a moderate AE will be reported and appropriate replacement therapy will be initiated. Repeat serum potassium levels will be obtained at 24 and 48 hours after start of replacement. If the levels do not normalize and the subject is asymptomatic, increased replacement will be initiated and the subject will be monitored closely. The clinical site PI will have the option to initiate study medication dose reduction (Section 4.F2). If the potassium is less than 2.5 mmol/L, a SAE will be reported, replacement therapy will be given immediately, and the study drug or placebo will be tapered and discontinued (Section 4.F3), unless another cause is identified as the cause for the hypokalemia (such as use of furosemide or another diuretic that may be used because of progression of liver disease and development of ascites).

7.D4. Impaired Wound Healing

Impaired wound healing is defined as a situation in which any of the following conditions are met:

- Readmission due to wound healing complications after discharge following portoenterostomy,
- Delay in discharge due to wound healing complications after portoenterostomy,
- Wound infection after portoenterostomy that requires specific treatment with antibiotics
- Return to the operating room in less than 30 days for wound management.
- A late complication in wound healing following portoenterostomy, such as, ventral hernia, ascitic leak, etc

Wound healing will be assessed daily in the hospital after portoenterostomy by the clinical team. A formal evaluation by the clinical site PI and study coordinator will occur on the day of discharge and at weeks 2 and 4 after portoenterostomy. Delay in discharge or readmission due to wound healing complications after surgery will be reported as an SAE. Wound infection that requires specific treatment with intravenous antibiotics will also be reported as a SAE. At outpatient study visits, an assessment will be made as to whether there is adequate wound healing. If there is a wound infection requiring surgical intervention in the operating room (i.e. reoperation) or complete wound dehiscence, it will be reported as a SAE. In the event of any SAE, drug or placebo will be tapered and discontinued (Section 4.F3). Care of the subject for impaired wound healing will be done according to local standard of care.

7.D5. Gastrointestinal Bleeding

If hematochezia, melena, hematemesis, or visible blood through nasogastric or gastrostomy tube is reported, an evaluation of gastrointestinal bleeding will be performed (e.g., to rule out anal fissure, infectious colitis, allergic colitis). If the bleeding is not associated with a drop in hematocrit and no further evaluation is indicated, a mild AE will be reported. If the presence of hematemesis, hematochezia or melena is associated with a drop in hematocrit of >5%, a moderate AE will be reported and further evaluation will be considered as clinically indicated; the clinical site PI will have the option to initiate study medication dose reduction (Section 4.F2). If a packed red blood cell transfusion is required and/or endoscopic intervention (such as sclerotherapy) is necessary, this will be reported as a SAE. The presence of a hemoglobin level < 6.5 g/dl or systemic hypotension caused by acute gastrointestinal bleeding will also be reported as a SAE, and the study drug or placebo will be tapered and discontinued (Section 4.F3).

7.D6. Pancreatitis

Because a single diagnostic test for pancreatitis is not available, a combination of tests and the best clinical judgment of the local PI will be used when evaluating the subject for possible pancreatitis. If there is new onset irritability presumed due to abdominal discomfort, progressive abdominal distension, inability to feed and/or vomiting, a serum lipase and/or pancreatic ultrasound will be ordered. If serum lipase is elevated (three times above the upper limit of normal) or ultrasound findings of pancreatitis are present⁸², this will be reported as a moderate AE; the clinical site PI will have the option to initiate study medication dose reduction (Section 4.F2). If the symptoms persist or require narcotic pain medication, or are associated with a pancreatic pseudocyst, hypocalcemia or anemia felt to be secondary to hemorrhagic pancreatitis, a SAE will be reported, and drug or placebo will be tapered and discontinued (Section 4.F3).

7.D7. Irritability

The development of severe irritability in the subject without an obvious cause will be considered a moderate AE, defined as the presence of inconsolable, persistent crying without an apparent cause, which requires evaluation and confirmation by the primary care provider or a visit to an emergency department if the subject is being followed as an outsubject, or by the clinical insubject team if the subject is in hospital at the time of the

event. Following evaluation for irritability and if no obvious cause is identified, a 50% dose reduction of study drug or placebo (Section 4.F2) will be considered by the clinical site PI. If the irritability resolves on this reduced dose, the duration of reduced dose will be the same as for the original dose, and the subject will continue to follow the remainder of the scheduled study drug/placebo regimen. The Medical Safety Officer will monitor all decreases in dose by clinical centers. If severe irritability persists despite the decrease in dosage, the study drug/placebo will be reduced by an additional 50%. If severe irritability persists despite this new reduction in dosage, the subject will undergo the tapering protocol and discontinuation of the study drug/placebo (Section 4.F3).

7.D8. Hypersensitivity Reaction to Trimethoprim-Sulfamethoxazole

If the subject develops a hypersensitivity reaction to TMP/SMZ manifested by a skin rash, the medication will be discontinued promptly and oral neomycin (25 mg/kg PO twice daily) will be used as prophylaxis against ascending cholangitis. Because neomycin provides no prophylaxis against PCP, the subject will also undergo a blinded taper. The study medication will be discontinued as outlined in (Section 4.F3) and the subject will continue to be followed per protocol even when off medication. Our choice to discontinue the study drug/placebo is based on concerns of the risk of PCP in the immunocompromised infant without TMP/SMZ prophylaxis.

7.D9. Cataracts

Cataracts are a well-recognized complication of long-term corticosteroid therapy, and are related both to dosage and duration of therapy. Children appear to be particularly at risk for steroid-induced cataracts. Despite the relative short duration of corticosteroid treatment in this clinical trial, all subjects will undergo an ophthalmologic examination at 12 months of age to monitor for the development of corticosteroid-induced posterior subcapsular cataracts. The examination will be performed by a pediatric ophthalmologist. The incidence of cataracts in corticosteroid treated-subjects and in placebo controls will be reported to the DSMB.

7.E. Vitamin Toxicity Monitoring

There is a potential risk of vitamin toxicity from supplementation. However, specific toxic concentrations of each of the fat-soluble vitamins are not available in the literature. Therefore, close monitoring of vitamin levels to confirm that they are not above the normal ranges reported by the laboratory is planned and outlined in section 4.N8 and 4.N9. Fat-soluble vitamin status will be checked within one month after starting supplementation through routine testing. Whenever a vitamin dose adjustment is made, follow-up testing will be performed within one month. If there is a major or rapid change in the severity of cholestasis (e.g., rapidly decreasing levels of serum bilirubin), vitamin levels will be monitored more frequently.

7.F. Adrenal Insufficiency:

During the taper: In the event of a life-threatening complication and when the physician treating the subject determines that knowing whether the subject was taking

corticosteroid is essential to implement his/her treatment plan (e.g., need for stress dose of steroid in the setting of bacteremia and hypotension or invasive tissue sepsis with systemic symptoms), the study code will be broken to reveal if the subject was receiving placebo or corticosteroids. [The Safety Monitor and the DCC will be informed immediately by the filing of a SAE report.] In this setting, if the subject had been receiving corticosteroids, the tapering protocol will typically use a stress dose of hydrocortisone (50-62.5 mg/m²/24h) for 2-3 days, then physiologic replacement (20-25 mg/m²/24h) for 7 days, then half of the replacement dose for 7 days; the use of hydrocortisone instead of prednisolone or methylprednisolone in the setting of infection will minimize additional immunosuppression that would result from the glucocorticoid action of prednisolone during the taper schedule. Alternatively, replacement doses may be in the form of prednisolone (using the doses outlined for weeks 2-8 of Table 5) if the subject tolerates oral/enteral feedings.

After the taper is completed: Although very unlikely, subjects may have some degree of adrenal suppression in the first year after the end of the steroid taper. Therefore, stress doses of hydrocortisone may also be used during the first year after the steroid taper in any subject that may show signs of adrenal insufficiency during a severe infectious illness or a significant stress event (such as surgery). The study code may only be broken to reveal if the subject was receiving placebo or corticosteroids if the physician treating the subject determines that knowing the information is necessary to implement his/her treatment plan. The Safety Monitor and the DCC will be informed immediately by the filling of a SAE report.

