5. STATISTICAL ANALYSIS AND DATA MANAGEMENT

5.A. Sample Size

5.A.1. Primary Endpoint

The primary endpoint (Hypothesis 1a) of this clinical trial is whether or not the subject has a serum total bilirubin <1.5 mg/dL with his/her native liver at 6 months after portoenterostomy. To determine the sample size for the clinical trial, we conducted a retrospective study of the level of serum total bilirubin and transplant-free survival in children with biliary atresia treated with portoenterostomy at the 14 ChiLDREN pediatric liver care centers. From the study, 54 of 118 infants (46%) had good bile drainage at 6 months, as determined by a serum total bilirubin level <1 mg/dL. (The results were tabulated at both 1 mg/dL and 2 mg/dL and the results were similar.) Our goal in this trial will be to improve the rate of good bile drainage at 6 months post-surgery from 50% to

75%. Using East-2000® (Cytel Software Company, Cambridge), a total of 110 subjects would need to be randomized to the two treatment groups in order to have 80% power to identify this difference at a 2-tailed 5% level of significance. To allow interim looks at the data after 50% and 75% of the subjects complete the trial using the O'Brien-Fleming spending function, the number of subjects that would be necessary is 114. To compensate for up to 20% attrition; we increased the sample size to a total of 140 subjects; e.g., 70 per group. Attrition will be defined as withdrawal by parents or guardians (which includes subjects who are lost to follow up) occurring within the first 6 months following portoenterostomy (prior to the time of evaluation of the primary outcome measure); however, data from all randomized subjects will be included in an intent-to-treat analysis.

5.A2. Secondary Endpoints

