Hypothesis 1b is that improved bile drainage, as determined by serum total bilirubin with native liver, will be improved in the infants treated with corticosteroids compared to those treated with placebo. Serum total bilirubin concentrations are measured at each clinical visit, including 3 and 6 months after portoenterostomy, and at 12, 18 and 24 months of age. (The time point of 6 months after portoenterostomy is the primary endpoint). A serum total bilirubin value >1.5 mg/dL, transplant or death, is indicative of failure of the portoenterostomy. The time to the first value >1.5 mg/dL (when the value is initially >1.5 and then declines to ≤ 1.5 , the time to the first value >1.5 mg/dL after the decline will be used), to transplant or to death will be considered time to failure of the procedure. The two groups will then be compared by a Cox regression model fitted to the time to failure. Since the test of the primary endpoint is a special case of this analysis, there is greater power for this comparison than for the primary endpoint.

Hypothesis 2 is that survival with native liver at 24 months of age is improved in infants treated with corticosteroids compared to those treated with placebo. In the 118 subjects in our survey of the ChiLDREN centers, 60 (51%) were transplanted by 24 months of age. Similar to the primary endpoint, we will have 80% power to show a 50% improvement in this measure (lowering the transplant rate from 50% to 25%).

Hypothesis 3 is that growth will be improved in infants treated with corticosteroids compared to those treated with placebo. These secondary endpoints, weight for age Z-score (in subjects without ascites) and height for age Z-score, are continuous. Children at the time of portoenterostomy are expected to have normal or near normal growth (mean Z-score near zero). Changes in weight and height Z-scores will be compared between treatment groups. For these endpoints there will be 80% power to identify a difference of 0.55 standard deviations (SD) between groups when 110 subjects are randomized. Since a mean Z-score of -1.0 or less would represent impaired growth and a mean > -0.5 would represent satisfactory growth, there will be almost 80% power to differentiate between these two outcomes.

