We do not have data to present power calculations for the other secondary endpoints (sufficiency of fat-soluble vitamins and incidence of ascites). We do not anticipate sufficient deaths by age 2 to compare survival between treatment groups.

5.A.3. Tertiary Endpoints

Tertiary endpoints are those that may be affected by improved liver function. The hypothesis is that infants treated with corticosteroids will have improved liver function at 12 and 24 months of age, which will result in lower INR, higher serum albumin, lower PELD score, higher platelet count, higher serum sodium concentration, lower serum bile acid concentration, lower PIVKA-II, higher mid-arm circumference and triceps skinfold thickness, better HRQOL, improved neurodevelopmental outcome, and adequate immunologic response to childhood immunizations. However, the study is not powered to detect differences in these variables. Therefore, analyses of these data will serve to generate specific hypothesis for future studies.

5.A.4. Interim Analysis

There are both short-term (e.g., bilirubin at 6 months post-portoenterostomy) and long-term outcomes (e.g., survival with a native liver and developmental assessments at 12 and 24 months of age). Although there is a relationship between bilirubin at 6 months and survival with a native liver, the intervention may impact these endpoints differentially and, especially, may impact development and growth in a manner independent of the level of bilirubin at 6 months. Therefore, the Steering Committee recommends that the trial should not be terminated early based on a test for either efficacy or futility. The Steering Committee recognizes that the DSMB will monitor adverse events and may recommend ending the study early if there is a significant imbalance in adverse events (risk to the participants) between the two treatment arms.

5.B. Data Analysis

General

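### The pooled AE/SAE comparison and the DSMB's cumulative AE summary mix transplant admissions, which are efficacy failures, with possible steroid harm

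*Protocol*

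**What the plan says.** - **Comparison.** Section 7.B1 notes that disease progression can itself cause events such as gastrointestinal bleeding, and concludes that "the frequency, severity and types of adverse effects, AEs and SAEs be compared between infants receiving study drug and those receiving placebo".
- **Definitions.** Under 7.B2 an AE counts whether or not it is judged related to the drug, and no time window is given. In 7.B3 one SAE criterion is "Requires insubject hospitalization or prolongation of an existing hospitalization". No exemption is made for transplant or for progression of liver disease. Table 8 (4.O3), in its row on infectious disease, has every hospitalization and emergency visit reported as an AE.
- **Duration.** Section 6.A3 limits steroid use to 13 weeks and keeps each infant in the trial to 24 months of age, which it puts at 18 to 24 months of participation.
- **DSMB summary.** Section 8 describes a quarterly running AE summary as a total plus a split by seriousness. It asks for no split by period or by transplant status.
- **Stopping.** Section 5.A.4 advises against stopping for efficacy or futility, and says that the DSMB "may recommend ending the study early if there is a significant imbalance in adverse events (risk to the participants) between the two treatment arms".
- **Transplant as outcome.** Section 5.B treats transplant as failure. In the survey of 118 infants in 5.A2, "60 (51%) were transplanted by 24 months of age", and the power statement there assumes a fall from 50% to 25%.

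**The concern.** Section 7.B1 handles the overlap between drug toxicity and disease progression by comparing the arms. That isolates toxicity only if progression is the same in both arms, and Hypothesis 2 says it will not be. If steroids delay transplant, the placebo arm collects more admissions for liver failure and transplant. Read literally, these are SAEs, and they offset any excess of infection, bleeding or wound problems on steroids. If steroids do not affect transplant, both arms carry the same load of disease-driven events and the drug signal is diluted.

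What is at stake is the interpretation of the pooled safety result. The DSMB reads it while the trial runs, and the risk-benefit assessment promised in Section 6.D needs harm measured apart from benefit.

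**Working it through.** **1. The plan's own figure.** Section 5.A.1 aims to "improve the rate of good bile drainage at 6 months post-surgery from 50% to" 75%, and states that "a total of 110 subjects would need to be randomized to the two treatment groups" for "80% power to identify this difference at a 2-tailed 5% level of significance". With unpooled variance:

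n per arm = (1.960 + 0.842)² × (0.50×0.50 + 0.75×0.25) / 0.25² = 54.9 with unrounded quantiles, so 55 per arm and 110 in total.

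The figure reproduces. The protocol then goes to 114 for interim looks and 140 (70 per arm) for attrition. It gives no figure for the AE/SAE comparison, so what follows illustrates the problem and corrects no stated number.

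**2. Transplants at the design rates.** Placebo 70 × 0.50 = 35; steroid 70 × 0.25 = 17.5. The survey rate agrees with the placebo assumption: 60/118 = 51%.

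**3. Any SAE by 24 months.** Let p be the risk of a non-transplant SAE and t the transplant risk. If they are independent, any-SAE = 1 − (1 − p)(1 − t). The documents give no SAE rates, so p is assumed: 20% placebo and 40% steroid.

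- Placebo: 1 − 0.80×0.50 = 60%
- Steroid, t = 25%: 1 − 0.60×0.75 = 55%
- Steroid, t = 40%: 1 − 0.60×0.60 = 64%
- Steroid, t = 50%: 1 − 0.60×0.50 = 70%

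The chance of a significant steroid-worse result at 70 per arm (two-sided 5%) is Φ((d − 1.96·se₀)/se₁). Here d is steroid minus placebo, se₀ is the pooled and se₁ the unpooled standard error. For 20% against 40%: (0.20 − 1.96×0.0775)/0.0756 = 0.64, giving 73.8%.

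| Transplant, placebo / steroid | Any SAE, placebo / steroid | Difference (points) | Chance of significant steroid-worse |
|---|---|---|---|
| excluded | 20% / 40% | +20 | 73.8% |
| 50% / 25% | 60% / 55% | −5 | 0.5% |
| 50% / 40% | 60% / 64% | +4 | 7.0% |
| 50% / 50% | 60% / 70% | +10 | 23.5% |

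**4. Range of assumed SAE risks, transplant 50% against 25%.**

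| Non-transplant SAE risk | Any SAE with transplant | Chance, transplant excluded | Chance, transplant counted |
|---|---|---|---|
| 10% / 25% | 55% / 43.8% | 64.9% | under 0.1% |
| 20% / 35% | 60% / 51.2% | 51.1% | 0.1% |
| 30% / 50% | 65% / 62.5% | 67.9% | 1.2% |
| 50% / 70% | 75% / 77.5% | 67.9% | 5.3% |

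The sign reverses in the first three rows. In the last it does not, but a 20-point harm shrinks to 2.5 points.

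**5. Independence.** Take 20% and 40% again, with the same overlap pattern in both arms. With transplant 50% against 25%, no overlap gives 20+50 = 70% against 40+25 = 65%, and full overlap gives 50% against 40%. Both reverse. With equal transplant rates, no overlap gives 70% against 90% (no dilution), and full overlap gives 50% against 50% (harm invisible).

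**6. Event counts instead of infants.** Assume 0.5 and 0.8 non-transplant SAEs per infant. Without transplants the totals are 70×0.5 = 35 and 70×0.8 = 56. With one SAE per transplant they are 70×(0.5+0.50) = 70 and 70×(0.8+0.25) = 73.5. With two per transplant they are 105 and 91, reversed. With equal transplant rates and one SAE each they are 70 and 91, so the 21-event excess remains but the ratio falls from 1.6 to 1.3.

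**7. Share of follow-up on drug.** 13 of 78 weeks (18 months) is 17%; 13 of 104 weeks (24 months) is 12.5%.

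**The case against.** The strongest reply is that AE windows, censoring and table layout usually belong to a statistical analysis plan, which was not available here. That holds for the layout of the final tables. But the protocol itself fixes the SAE criterion, the content of the DSMB summary and the stopping language, and those parts already mix the two quantities.

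Second, 7.B1 asks for comparison by severity and type, and 7.D gives wound healing, bleeding, pancreatitis and other steroid effects their own definitions. Section 4.O3 does the same for infection, and every SAE report goes to the DSMB. This stands and limits the damage: a careful board could see the signal by type. It does not remove the mixing from the pooled comparison or from the cumulative summary.

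Third, a transplant is a procedure, and 7.B2 ties AEs in time to use of the product, so some sites might not report transplant admissions as SAEs. The Table 8 line also sits in an infection row. That is fair, but the text then leaves sites free to report differently.

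Fourth, the SAE risks are assumed and the transplant rates are 24-month design targets. At early DSMB reviews fewer transplants will have occurred, so the distortion is smaller then and grows with follow-up.

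**Conclusion.** The concern holds for the pooled AE/SAE comparison and the cumulative DSMB summary. At the design's own rates, transplant alone could add an SAE for 35 placebo against 17.5 steroid infants. Under the assumed 20% against 40% non-transplant risks and independence, a 20-point harm appears as a 5-point advantage if the full transplant benefit occurs, and as a 10-point harm if there is none. Reversal therefore needs a sizeable transplant benefit; without one, independence gives dilution only.

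Stronger readings that the documents do not support:

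- A reader might infer that an AE imbalance is the only possible ground for early stopping. It is the only between-arm criterion named in 5.A.4, but that is a Steering Committee recommendation. Section 8 has the DSMB monitor efficacy among other things and lets it recommend termination.
- A reader might infer that post-transplant events certainly enter the count. The trial gives no rule. Participation to 24 months of age suggests that they do, while the companion database (3.A5) ends follow-up at transplant.
- A reader might extend the point to the 12-month eye examination in 7.D9. The documents give no mechanism by which transplanted infants would bias the cataract comparison.

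**What to change.** In Sections 7.B1 and 8:

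1. Keep the all-event AE/SAE table to 24 months of age.
2. Add by-arm tabulations of AEs and SAEs (a) during study drug and a stated short period after it, and (b) later but before transplant.
3. List transplant admissions and any post-transplant events separately as outcomes, outside the SAE imbalance that the DSMB judges.
4. State whether AEs are collected after transplant, so that sites report alike.

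The on-drug table should supplement the all-event table and not replace it. Section 6.D sets out to study long-term harm, and 7.F allows for adrenal suppression in the first year after the taper, so a short window alone would miss events that the protocol wants to see. Ending a count at transplant also conditions on something that treatment may affect, which is another reason to keep the full table.

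The cost is a few sentences and a little more table programming, with fewer events in each sub-table. Table 6 already has a transplant visit, and AE end dates are recorded under 7.C.
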